9.7.2 Methods of analysis

9.7.2.1 Primary safety endpoint

Incidence of (1) significant elevations of liver enzymes ALT, and/or AST, and/or GGT (≥3 times ULN) and/or bilirubin (>2 times ULN), and (2) treatment-emergent hepatobiliary adverse drug reactions in Part A (i.e. first 6 months of treatment).

9.7.2.2 Secondary safety endpoints

- Incidence of (1) significant elevations of liver enzymes ALT, and/or AST, and/or GGT (≥3 times ULN) and/or bilirubin (>2 times ULN), and (2) treatment-emergent hepatobiliary adverse drug reactions over the entire study period.
- Incidence of cardiovascular adverse events (i.e. thromboembolic adverse events and MACE) during PART A and over the entire study period.

9.7.2.3 Additional endpoints

- Incidence of all treatment-emergent adverse events
- Incidence of adverse events of special interest
- Duration of significant elevation of liver parameters

9.7.2.4 Effectiveness of risk minimization measure endpoints:

- Frequency of evaluation of liver enzymes (AST, ALT, GGT) and bilirubin
- Frequency of dose adjustments or treatment discontinuation in case of hepatotoxicity
- Rate of hepatobiliary adverse events after dose reduction or treatment discontinuation due to significant elevations of liver enzymes ALT, and/or AST, and/or GGT (≥3 times ULN) and/or bilirubin (>2 times ULN)
- Rate of liver enzyme/bilirubin normalization after dose reduction or discontinuation due to significant elevations of liver enzymes ALT, and/or AST, and/or GGT (≥3 times ULN) and/or bilirubin (>2 times ULN)
- Time to liver enzyme/bilirubin normalization after dose reduction or discontinuation due to significant elevations of liver enzymes ALT, and/or AST, and/or GGT (≥3 times ULN) and/or bilirubin (>2 times ULN)
- Rate of hepatobiliary adverse event resolution after dose reduction or discontinuation due to treatment-emergent hepatobiliary adverse drug reaction
- Time to hepatobiliary adverse event resolution after dose reduction or discontinuation due to treatment-emergent hepatobiliary adverse drug
- Number of patients with hepatobiliary adverse events after significant elevations of liver enzymes ALT, and/or AST, and/or GGT (≥3 times ULN) and/or bilirubin (>2 times ULN)

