Polycythaemia vera (PV), a myeloproliferative neoplasm, is a very rare disease and typically develops in late adulthood. It is an acquired form of primary erythrocytosis which is characterized by an excess production of erythrocytes, leukocytes and platelets.

Ropeginterferon alfa-2b belongs to the pharmacotherapeutic group of antineoplastic and immunostimulating agents, immunostimulants; interferons (IFNs). Ropeginterferon alfa-2b is the first IFN indicated as monotherapy in adults for the treatment of PV without symptomatic splenomegaly.

The general safety profile of ropeginterferon alfa-2b can be seen as well characterized and safety data provided for ropeginterferon alfa-2b can be compared with that of already approved IFN products.

Hepatic safety

Hepatotoxicity is a well-known safety class effect of IFNs¹ (including cases of drug-induced liver injury [DILI]) characterized by potentially significant increases in liver enzymes. Hepatotoxicity has to be considered as the most clinically relevant toxicity of IFNs, including also ropeginterferon alfa-2b.

¹ Hepatotoxicity is included as important, identified safety concern in the EMA approved Risk Management Plan for ropeginterferon alfa-2b (Version 1.0, dated 13DEC2018).

Increases in alanine aminotransferase (ALT) (≥ 3 times the upper limit of normal), aspartate aminotransferase (AST) (≥ 3 times the upper limit of normal), gamma-glutamyl transferase (GGT) (≥ 3 times the upper limit of normal) and bilirubin (> 2 times the upper limit of normal) levels have been observed in patients treated with ropeginterferon alfa-2b. These elevations were mostly transient and occurred during the first treatment year.

Cardiovascular safety

Thromboembolic events are rare events but appear significantly more frequent in PV patients than in the healthy population and are a major risk of this disease.

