The effectiveness of the routine risk communication to address dose adjustment or treatment discontinuation in case of hepatotoxicity, as described in section 4.2 and 4.4 of the SmPC, will be evaluated by assessing rate of dose adjustments or treatment discontinuations due to hepatoxicity, the rate of hepatobiliary adverse events occurring despite dose reduction or treatment discontinuation due to elevated liver enzymes, the rate of, and time to resolution of significant elevations of ALT, AST, GGT (≥3 times ULN) and/or bilirubin (> 2 times ULN) and/or hepatobiliary adverse drug reactions as well as the number of patients experiencing

hepotobiliary adverse events after significant elevations of liver enzymes ALT, and/or AST, and/or GGT (≥3 times ULN) and/or bilirubin (>2 times ULN).

Endpoints for the evaluation of effectiveness of risk minimization measurements for the important, identified risk "hepatotoxicity":

- Evaluations of liver enzymes (i.e. ALT, AST, GGT), and bilirubin in routine clinical practice
- Hepatobiliary adverse events after dose reduction or treatment discontinuation due to elevated liver enzymes
- Dose reduction or treatment discontinuation due to hepatotoxicity
- Liver enzymes (i.e. ALT, AST, GGT), and bilirubin after dose reduction or treatment discontinuation
- Treatment-emergent hepatobiliary adverse drug reactions after dose reduction or treatment discontinuation
- Number of patients with hepatobiliary adverse events after significant elevations of liver enzymes ALT, and/or AST, and/or GGT (≥3 times ULN) and/or bilirubin (>2 times ULN)

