9.2.8 Patient 's dose change/ dose interruption

The recommendations in the product information for ropeginterferon alfa-2b dosing (including dose changes or temporarily treatment interruption) should be followed (Annex 1). Any ropeginterferon alfa-2b dose change/interruption has to be documented including the reason for

dose change/interruption. A temporary ropeginterferon alfa-2b treatment interruption is no reason for study discontinuation.

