9.3.2 Evaluation of risk minimization measures

- Frequency of evaluation of hepatic enzymes (AST, ALT, GGT) and bilirubin in clinical routine
- Hepatobiliary adverse events after dose reduction or treatment discontinuation due to significant elevations of liver enzymes ALT, and/or AST, and/or GGT (≥3 times ULN) and/or bilirubin (>2 times ULN)
- Dose adjustments or treatment discontinuations due to hepatotoxicity
- Hepatic enzymes (AST, ALT, GGT) and bilirubin after dose reduction or treatment discontinuation due to significant elevations of ALT, AST, GGT (≥3 times ULN) and/or bilirubin (> 2 times ULN)
- Follow-up of hepatobiliary AEs after dose reduction or treatment discontinuation due to Treatment-emergent hepatobiliary adverse drug reactions

Important identified risk in the ropeginterferon alfa-2b Risk Management Plan.

 Number of patients with hepatobiliary adverse events after significant elevations of liver enzymes ALT, and/or AST, and/or GGT (≥3 times ULN) and/or bilirubin (>2 times ULN)

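### The liver-recovery endpoints in 9.7.2.4 cover only patients with a dose reduction or discontinuation, which conflicts with 9.1 and omits temporary interruption and no action

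*Protocol*

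**What the plan says.** Evaluating the effectiveness of the risk minimisation measures for hepatotoxicity is a secondary objective (Protocol Section 8). Section 7 says that the evaluation concerns the product-information recommendations on monitoring liver enzymes and on adjusting dose.

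The descriptive text in 9.1 includes the rate of, and time to, resolution of significant elevations and of hepatobiliary adverse drug reactions. It attaches no condition on the action taken. The endpoint list that follows in 9.1 is narrower: "Liver enzymes (i.e. ALT, AST, GGT), and bilirubin after dose reduction or treatment discontinuation". Section 9.3.2 repeats the restriction: "Hepatic enzymes (AST, ALT, GGT) and bilirubin after dose reduction or treatment discontinuation due to significant elevations of ALT, AST, GGT".

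The analysis endpoints in 9.7.2.4 carry the same condition:

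- "Rate of liver enzyme/bilirubin normalization after dose reduction or discontinuation due to significant elevations of liver enzymes ALT"
- "Time to liver enzyme/bilirubin normalization after dose reduction or discontinuation due to significant elevations of liver enzymes ALT"
- "Rate of hepatobiliary adverse event resolution after dose reduction or discontinuation due to treatment-emergent hepatobiliary adverse drug reaction"

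The time to adverse event resolution and the rate of hepatobiliary adverse events after action are restricted in the same way.

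Section 9.2.8 refers to dosing recommendations that include "dose changes or temporarily treatment interruption". It requires every change or interruption to be documented with its reason, and adds: "A temporary ropeginterferon alfa-2b treatment interruption is no reason for study discontinuation". On the liver elevations seen so far, Section 7 says: "These elevations were mostly transient and occurred during the first treatment year".

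**The concern.** Consider two patients with the same significant elevation. In one, injections are paused and later resumed at the same dose. In the other, nothing is changed. Read literally, neither enters the normalisation or resolution endpoints, although the text of 9.1 would count both.

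Two things are at stake. First, the denominator of the recovery endpoints depends on which section the analyst follows. Second, recovery would be reported only for patients in whom the dose was reduced or treatment stopped. If most elevations are transient, a high normalisation rate in that group is hard to read without the rate in the other patients beside it. A reader of the final report could credit the recommendation with recovery that would have happened anyway.

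**Working it through.** **Step 1. Conditions on the eight endpoints in 9.7.2.4.**

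| Endpoint (paraphrased) | Trigger | Limited to reduction or discontinuation? |
|---|---|---|
| Frequency of liver tests | none | no |
| Frequency of dose adjustment or discontinuation | hepatotoxicity | no |
| Rate of hepatobiliary AEs after action | laboratory elevation | yes |
| Normalisation rate | laboratory elevation | yes |
| Time to normalisation | laboratory elevation | yes |
| Rate of AE resolution | hepatobiliary ADR | yes |
| Time to AE resolution | hepatobiliary ADR | yes |
| Number of patients with hepatobiliary AEs after elevation | laboratory elevation | no |

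Five are restricted (four on recovery, one on later events) and three are not. The duration of significant elevations in 9.7.2.3 is also unrestricted.

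**Step 2. Can interruption be read into the restricted wording?**

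- As discontinuation: no. Section 9.2.7 equates stopping the drug with leaving the study, while 9.2.8 says that an interruption does not end participation.
- As dose reduction: not on the plain words. Section 9.2.8 names dose changes and interruption as alternatives.
- As dose adjustment: possibly, but that broader term appears only in the frequency endpoint. A paused patient could be counted there as managed and still be absent from all five restricted endpoints.

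**Step 3. Who is followed for recovery?**

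| Management of the event | 9.1 text | 9.3.2 and 9.7.2.4 |
|---|---|---|
| Dose reduced | yes | yes |
| Treatment discontinued | yes | yes |
| Interrupted, resumed at the same dose | yes | no |
| No action | yes | no |

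A patient who is first interrupted and later reduced or stopped because of the same elevation would enter the restricted endpoints.

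**Step 4. Order of magnitude (illustration only).**

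The plan states no figure for these endpoints. Inputs from 9.5: one-year incidence of significant laboratory increases 23.6%; 178 evaluable patients. Assuming a constant hazard:

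- 6 months: 1 − (1 − 0.236)^0.5 = 12.6%, which reproduces the protocol's figure; 178 × 0.126 ≈ 22 patients.
- 18 months: 1 − (1 − 0.236)^1.5 = 33.2%; 178 × 0.332 ≈ 59 patients.

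The protocol does not say how often elevations lead to each action. The share with a reduction or discontinuation is therefore varied as an assumption. Widths are of exact (Clopper-Pearson) 95% intervals at an assumed normalisation rate of 80%.

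| Assumed share | Contribute | Left out | 95% CI width |
|---|---|---|---|
| 20% | 12 | 47 | 0.46 |
| 40% | 24 | 35 | 0.35 |
| 60% | 35 | 24 | 0.29 |
| 80% | 47 | 12 | 0.24 |
| 100% | 59 | 0 | 0.22 |

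This applies only to the three restricted endpoints triggered by a laboratory elevation. The two AE-resolution endpoints are triggered by a hepatobiliary ADR, for which the protocol gives no incidence, so no count can be offered for them.

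**The case against.** The other side has a substantial case.

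- **The evaluation does not rest on these endpoints alone.** Section 7 sets the target as monitoring and dose adjustment, and the two frequency endpoints measure those directly. The count of patients with hepatobiliary events after an elevation applies whatever was done, and 9.7.2.3 covers the duration of all elevations. This stands. A reader might infer that the study cannot show whether the measures work; the protocol does not support that.
- **Nothing visible shows that recommended liver management is being dropped.** Section 9.2.8 speaks of dosing in general. Where 9.1 describes the advice for hepatotoxicity, it names dose adjustment and discontinuation. The product information is a stand-alone document and is not reproduced. This stands too: the finding is that a recorded action has no place in the recovery endpoints, not that compliant care is excluded.
- **A split by action will not establish cause.** The study has no control group, as 9.9 acknowledges, and patients in whom action is taken will differ in severity. This is correct and limits what the change can deliver. It can supply a descriptive reference, not proof.
- **Table layout belongs in the SAP.** This is true of the layout. It does not answer the point that the protocol itself fixes the endpoint populations, and fixes them differently in 9.1 and in 9.3.2 and 9.7.2.4.

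**Conclusion.** The point holds in a limited form. The text of 9.1 covers resolution of all significant elevations, while 9.3.2 and five of the eight endpoints in 9.7.2.4 narrow recovery and later hepatobiliary events to patients with a dose reduction or discontinuation. Interrupted patients who resume at the same dose, and patients with no action, fall outside the normalisation and resolution endpoints. Recovery is therefore shown without a descriptive reference.

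The finding about the wording rests on the protocol alone. Its size does not. The range of 12 to 47 contributing patients out of about 59 assumes a constant hazard, 178 patients followed for 18 months, and action shares of 20% to 80% that nothing in the protocol informs. A reader might conclude from such figures that most affected patients are lost; the protocol supports neither that conclusion nor its opposite.

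The primary endpoint is unaffected. One secondary objective is measured incompletely, on a denominator that the protocol defines in two ways. This concerns analysis definitions only and implies no view on which clinical action is right.

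**What to change.** 1. Reconcile 9.1, 9.2.8, 9.3.2 and 9.7.2.4 so that they name the same population for the recovery endpoints.
2. State that temporary interruption counts as an action for these endpoints, and whether it falls under dose adjustment in the frequency endpoint.
3. Report the normalisation rate, time to normalisation and subsequent hepatobiliary adverse events for every patient with a first significant elevation. Report the rate of and time to adverse event resolution for every patient with a hepatobiliary adverse drug reaction.
4. Tabulate both by action taken (none, reduction, interruption, discontinuation), and label the comparison descriptive, not causal.

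The cost is wording in the protocol and SAP and one added breakdown. No new treatment data are needed: 9.2.8 already records changes and interruptions with reasons, and 11.2 records the action taken for each adverse event. The downside is that the groups will be small and will differ in severity, so between-group differences must not be read as effects of the action.

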9.7.2.5 Additional subgroup analyses

- Subgroup analysis of incidence of significant elevations of liver enzymes and bilirubin for patients with and without co-medication with nonsteroidal anti-inflammatory drugs
- Subgroup analysis of incidence of significant elevations of liver enzymes and bilirubin for patients with and without pre-existing liver disease/or patients with baseline liver parameter elevation
- Subgroup analysis of incidence of treatment-emergent hepatobiliary adverse drug reactions for patients with and without co-medication with nonsteroidal anti-

inflammatory drugs

- Subgroup analysis of incidence of treatment-emergent hepatobiliary adverse drug reactions for patients with and without pre-existing liver disease/or patients with baseline liver parameter elevation
- Subgroup analysis of incidence of cardiovascular events (i.e. thrombo-embolic adverse events and MACE) for patients with and without cardiovascular risk factors
- Subgroup analysis of incidence of cardiovascular events (i.e. thrombo-embolic adverse events and MACE) for patients with and without pre-existing cardiovascular disease

Absolute and relative frequencies of patients with treatment emergent adverse events, count and incidence rate (including two-sided 95% CIs) of events overall and by MedDRA primary System Organ Class and Preferred Term will be calculated.

In addition, tables will be prepared to list each serious and non-serious adverse event, the number of patients who experience an event at least once, and the proportion of patients with adverse events/serious adverse events/adverse events of special interest.

Adverse events will be grouped by system organ class (SOC). Each event will be then divided into defined intensity grades (mild, moderate, and severe) by the Investigator. The tables will also divide the adverse events into those considered related to treatment (ropeginterferon alfa-2b) and those not related, as well as adverse events considered related to underlying disease PV.

The statistical analysis will be done in agreement with the ICH Topic E9, Statistical Principles for Clinical Trials and Statistical Analysis Plan (SAP) finalized and approved by the Sponsor and the study statistician before database lock. Analyses will be conducted using Statistical Analysis System (STATA®) software,

by using the last version of the dictionaries available at that timepoint.

9.7.3 Planned interim analysis of the study

An interim analysis is planned after finalization of Part A of the study.

9.8. Quality control

The sites in each country will be selected based on the availability of patient population targeted for this study.

The selected Investigators and study sites will have the ability to appropriately conduct this study in accordance with applicable legal and regulatory requirements.

9.8.1 Investigator 's responsibility

- The Investigator will comply with the study protocol, applicable local regulatory requirements and with the ethical principles that have their origin in the Declaration of Helsinki.
- The Investigator is responsible for the conduct of the study at the study site.
- If any responsibilities are delegated, the Investigator should maintain a list of appropriately qualified persons to whom he/she has delegated significant study-related duties.

9.8.2 Direct access to source data/records

• The Investigator guarantees that the Monitors, Auditors, members of the EC, authorized

personnel of the Sponsor or regulatory authorities will have direct access to all relevant source data/documents and patients' medical records providing that the confidentiality of patients is preserved.

9.8.3 Study monitoring and source data verification

- The Sponsor will nominate a qualified Monitor to maintain a close contact with the Investigator and study staff to ensure the study is being conducted in accordance with the protocol, regulatory requirements and local law and that GCP guidelines will be followed whenever possible to reach high standard of quality. This liaison will consist of regular documented personal visits, and/or telephone or e-mail communication prior to study initiation and at regular intervals during the study.
- The Monitor will arrange regular visits to the study centre(s) to check and confirm the completeness of patient records, the accuracy of entries in the eCRFs, consistency of source data with the eCRF entries, the adherence to the protocol and that GCP guidelines will be followed whenever possible to reach high standard of quality.
- The Monitor will ensure that the Investigator/study team personnel understand the protocol requirements and the regulatory responsibilities as an Investigator.
- Key study team personnel should be available to assist the responsible Monitor during these visits and correct the errors found by the Monitor in eCRFs and/or other documents pertinent to the project.
- The Monitor will also check the completeness of the Investigator site file (ISF) and related documentation (e.g. team delegation log).
- The Sponsor monitoring standards require full verification for the presence of Informed Consent, adherence to the inclusion/exclusion criteria, and the recording of the study objective. Details will be described in the study-specific monitoring plan.

9.8.4 Auditing

• The study may be audited by the Sponsor or inspected by regulatory authorities during the study and/or after study completion. The Investigator will permit and fully cooperate with the Sponsor during audits, EC review(s) and/or regulatory inspection(s), and provide direct access to all study relevant documents and data.

9.9. Limitations of the research methods

Data are captured in real-world setting. Patients may be exposed to a multitude of other medical procedures, are aware of their treatment and are not compared to a control group. Due the observational nature of the study, it should be taken into consideration that there might be incomplete datasets among the participating centres.

The Sponsor has selected approximately 10 Sites in Austria and 15 sites in Germany, covering a large proportion of the pool of suitable patients in both countries, to participate in this study. In the unlikely case of slow recruitment, the Sponsor will evaluate the inclusion of additional sites and assess the possibility of adding sites in additional countries, depending on the status of commercialization of Besremi.

The primary endpoint of the Besremi-PASS study is the incidence of significant elevations of liver enzymes ALT, and/or AST, and/or GGT (≥3 times ULN) and/or bilirubin (>2 times ULN), and (2) treatment-emergent hepatobiliary adverse drug reactions in the first 6 months of treatment. A dropout rate of 20% over one year was observed in the PROUD-PV study, from which a dropout rate of 10% can be assumed after 6 months of treatment. The extrapolated dropout rate of 28.5% over 18 months used for sample size calculations is therefore highly conservative and will allow for evaluation of the primary endpoint even if dropout rates over 6 months of treatment are higher than expected.

9.10 Other aspects

Not applicable; all aspects of the study are described in the other protocol sections.

10. Protection of human subjects

Due to the non-interventional nature of this study, patients are not exposed to any study-specific medical procedures, and therefore to no study-specific medical risk.

